6. RECRUITMENT METHODS

For this study, we will partner with schools (e.g., Hackensack High School) and community-based organizations (e.g., Ibero American Action League) to identify and refer potential adolescents. We plan to advertise this study via printed and electronic materials (e.g., study flyers). Parents/caregivers interested will be referred to research staff to obtain parent permission and child assent. Our research team consists of a culturally diverse group of Latinos and African Americans, which will help build rapport with the participants and their parents/caregivers.

7. CONSENT PROCESS

We will not obtain written informed consent for participating in this study. Instead, we will provide informational sheets to both the parents/guardians and the adolescents. In accordance with Police 701 of Informed Consent, this study requests a waiver of documentation because the research involves no more than minimal risk and involves procedures for which written consent is normally required outside the research context. This study represents no greater than minimal risk because it is a study of a non-sensitive nature. We will obtain parents'/guardians' permission over the phone. Then, we will obtain adolescents' assent via REDCap by clicking "Yes, I assent to participate in the study" after reading the informational sheet. The informational letter will also contain language describing the study, the risk and benefits, and team contact information in case they have questions. Adolescents will also have the opportunity to discuss the study and ask questions by contacting the research staff. Participants will be informed that their participation is completely confidential and voluntary, and that participation may end at any time during the assessment. If an individual chooses to stop participation or withdraw from the study, the de-identified data collected will be kept by the study team.

8. STUDY PROCEDURES

Once parents'/guardians' permission and adolescent's assent has been obtained, participants (n=360) will complete an individual baseline assessment on sociodemographic characteristics and susceptibility to future vaping. The survey will be hosted in REDCap, a secure, web-based system that has user-level access control. Each participant will receive a unique username and password to access the survey. At the end of the baseline assessment, participants will be randomized in equal number and representation to receive one of four (4) graphic messages: 1) health reward, 2) financial reward, 3) self-efficacy, and 4) social norms. The appropriate graphic message, available in English and Spanish, will be displayed in REDCap. Participants will be instructed to view the graphic messages carefully on their devices (e.g., desktop, laptop, tablet, and/or smartphone) and for as long as they wish. We will assess immediate post-exposure measures on susceptibility to future vaping (primary outcome). Study measures on susceptibility to future vaping are comprised of valid items derived from out and others' research. We will assess three items: (1) Are you curious about using e-cigarettes (vaping)?; (2) Do you think that you will use e-cigarettes (vaping) in the next 12 months?; and (3) If one of your best friends were to offer you an e-cigarette, would you use it? Responses include 1= definitely not, 2= probably not, 3= probably yes, 4= definitely yes. Participants will receive \$25 gift card for their time at the end of the assessment.

9. RISK TO SUBJECTS

The risk for this study is minimal. Loss of privacy of personal information is a small risk. Only [name] (Principal Investigator) and research team will have access to study data. **Adequacy of Protection against Risks.** Issues covered in the information sheet will include a description of study procedures, the time involved, the right to withdraw at any time without penalty, procedures used to protect participant anonymity, use of data, and potential benefits and risks of participating in the study.

10. POTENTIAL BENEFITS TO SUBJECTS

Participation in this study may prevent subjects from vaping. Moreover, this study will examine the effectiveness of newly designed, theoretical-based graphic messages at preventing future vaping use among African American and Latino adolescents.

11. COSTS FOR PARTICIPATION

Participation in this study is at no financial cost to the participants.

12. PAYMENT FOR PARTICIPATION

Subjects will be compensated for their participation in the study by receiving a \$25 gift card. In order to maintain anonymity of subject participants, those who complete the survey will be redirected to a code to claim an Amazon® gift card.

13. SUBJECT WITHDRAWALS

Subjects will be informed that they may withdraw from the study at any time without prejudice and compilation of that person's data will cease as of the date of his/her written request for withdrawal. It is possible that individuals might not want to participate and/or may withdraw from the study, and that is their right. If a subject withdraws before completing the three phases, data collected until the point of withdrawal remains part of the study database and may not be removed. Other subjects will replace subjects withdrawn from the study. We do not anticipate any circumstances in which subjects will be withdrawn from the research without their consent.

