17. DATA ANALYSIS PLAN

We first will perform descriptive statistics to evaluate randomization success, nonresponses, and missing data. Mean and median will be presented for continuous variables, and frequencies will be presented for categorical variables. The outcome measures will be defined as (1) a binary variable of susceptibility to future vaping (0= definitely not, 1= probably not, probably yes, definitely yes) to ease interpretation of results, and (2) the overall susceptibility score aggregating three items. Bivariate analyses will be performed, followed by multivariable modeling to compare different message groups. Logistic regression model and the analysis of covariance (ANCOVA), respectively, will be performed to control for potential confounding, and inflated type I error rate will be adjusted in multiple testing. We will also assess differences within messages by theoretical construct (reward, self-efficacy, and social norms). **Power Analysis.** The goal of this pilot analysis is to provide preliminary data for future studies, including the possible effect size. Using the ANCOVA analysis for the power calculation, we expect the effect size to be 1.05 (standardized mean difference in the aggregated score) between message groups.

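### Does replacing withdrawn subjects, possibly including some already randomised to a message, distort the comparison of the four messages?

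*Combined protocol and SAP*

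**What the plan says.** Section 13 (Subject Withdrawals) gives the replacement rule without qualification: "Other subjects will replace subjects withdrawn from the study". The sentence before it deals with data already collected: "If a subject withdraws before completing the three phases, data collected until the point of withdrawal remains part of the study database". The same section ties the end of data collection to a written request from the subject.

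Section 7 (Consent Process) tells subjects that "participation may end at any time during the assessment", and it mentions stopping and withdrawing as two separate things.

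Section 8 (Study Procedures) sets the order of events: "At the end of the baseline assessment, participants will be randomized in equal number and representation". The message is then displayed and the primary outcome is taken immediately afterwards, in the same REDCap survey. Under section 12, "those who complete the survey will be redirected to a code to claim" a gift card.

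Section 17 (Data Analysis Plan) opens with "descriptive statistics to evaluate randomization success, nonresponses, and missing data". It then plans logistic regression and ANCOVA to compare messages. It defines no analysis set and does not mention withdrawals by message. Section 4 (Study Design) fixes 360 subjects, 180 African American and 180 Latino, in equal numbers across four messages, which is 90 per message.

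**The concern.** Once a subject has been assigned a message, whether that subject counts should not depend on what happens next. Read literally, section 13 allows someone to be randomised, see a message, leave, and be replaced by a new recruit. With no analysis set in section 17, a reader may suppose that the final analysis will be of 360 completers.

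Two things would be at stake. If one message drives off the more susceptible adolescents, those who remain in that group look less susceptible and the message looks better than it is. And topping up to the target could hide the fact that one message lost more people, which would itself be a finding about that message.

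**Working it through.** **Does the rule reach randomised subjects?** By the order of events in section 8 it can, but this is an inference. Section 13 speaks of withdrawal by written request. An adolescent who closes the browser between the message and the questions has stopped; it is not clear that this is a withdrawal in that sense. Such break-offs fit the nonresponse and missing data that section 17 will describe.

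**Does replacement create bias?** Let w be the fraction leaving a message group and D the leaver-minus-completer difference in mean score. The completer mean is the group mean minus w × D, whether the group ends with 81 completers or is topped up to 90. The bias in a comparison of messages A and B therefore has size (w_A − w_B) × D, and the number of replacements does not enter. This holds as long as later recruits come from the same population and are randomised in the same way.

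**How large could the missing-outcome bias be?** The plan gives no withdrawal rate, so these inputs are assumptions: losses of 10% v 2% or 15% v 5%, and D of 0.5 to 1 SD.

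- Unadjusted: 0.08 × 0.5 = 0.04; 0.08 × 1 = 0.08; 0.10 × 1 = 0.10 SD.
- With the baseline score in the ANCOVA, and leaving driven by the post-exposure score, multiply by (1 − r²), where r is the baseline-post correlation (assumed 0.5 to 0.8): 0.04 × (1 − 0.64) = 0.014, up to 0.10 × (1 − 0.25) = 0.075 SD.
- If leaving depends only on the baseline score, the adjusted bias is about 0.

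A simulation (4000 runs per case, 90 per arm) gave 0.014 to 0.082 SD after adjustment, and results with and without replacement agreed within 0.01 SD in every case. A separate simulation gave −0.087 without v −0.088 with replacement unadjusted, and −0.053 v −0.055 adjusted. Against the planned effect of 1.05 the largest values are 0.10/1.05 = 10% before adjustment and 0.082/1.05 = 8% after.

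**How many replacements would there be?** With fresh allocation until 360 complete:

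- 10% v 2%: mean loss (0.10 + 3 × 0.02)/4 = 0.04, and 360/0.96 = 375 randomised. That is 15 leavers, about 9 from one message and 2 from each other.
- 15% v 5%: mean loss (0.15 + 3 × 0.05)/4 = 0.075, and 360/0.925 = 389 randomised. That is 29 leavers, about 15 and 5.

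**What would restricting replacement do?** With 360 randomised and losses of 10% v 2%, the groups keep 90 × 0.90 = 81 and 90 × 0.98 = 88 outcomes. The total is 81 + 3 × 88 = 345 instead of 360. The difference detectable with 80% power (two-sided t test; alpha assumed, since none is stated) moves from 0.42 to 0.43 SD at 0.05, and from 0.52 to 0.54 SD at 0.05/6. For an effect of 1.05 the t test needs 16 or 24 per arm, so power is not the reason to keep or drop the rule. Estimates stay the same; what is lost is the equal group sizes and the 180/180 split among subjects with an outcome.

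**The case for a change.** The best case for a change is that it is cheap and makes the plan explicit. A few sentences would limit replacement to withdrawals before randomisation, keep everyone randomised in the assigned group, send later recruits to the next allocation, and require withdrawals by message. Section 17 calls this a pilot analysis meant to supply an effect size for later studies, so the denominator behind that effect size should be visible. The plan does not say whether a replacement takes the vacated slot or the next allocation. And since power at 1.05 exceeds 99.9% even with 81 v 88, replacement is not needed for precision.

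Part of this stands. The analysis set is not named, by-message loss is not promised, and the sentence in section 13 has no timing limit. But these are gaps in detail, and none shows replacement doing harm. Data up to withdrawal are kept, so everyone randomised can be counted by message. Section 17 places nonresponse and missing data in the same step as the check on randomisation, which is naturally made by group. That 360 completers alone would be analysed is a supposition; no section says it.

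Power is also not the only purpose that replacement can serve: section 4 commits to equal numbers and representation, and continued recruitment helps to meet that. Two further proposals go beyond the point. Naming the baseline score as a covariate only spells out what an ANCOVA of a pre/post design already implies, and filling missing outcomes with no change from baseline is one preference among several.

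**Conclusion.** The concern does not call for a change. Replacement adds no bias of its own, and rewriting section 13 would leave every estimate materially where it is while working against the planned equal numbers. What remains is bias from missing outcomes, identical with or without replacement: at most 0.10 SD unadjusted and about 0 to 0.08 SD adjusted, against 1.05. Those figures rest on assumed differential losses of 8 to 10 points and on leavers scoring 0.5 to 1 SD higher, neither of which the documents support. One online session, an outcome taken at once and a gift card for completers all suggest that loss after randomisation will be rare and the bias near zero.

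The conclusion also assumes that later recruits are randomised like everyone else, and that the analyst counts all randomised subjects in their assigned message, analyses those with an outcome, and shows losses by message. That is ordinary practice and the retained data allow it.

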14. PRIVACY AND CONFIDENTIALITY OF SUBJECTS AND RESEARCH DATA

The PI and research staff have completed all required training through the Collaborative Institutional Training Initiative (CITI), including the Human Subjects Protection and Good Clinical Practice Training. Subjects will be limited to interactions with the research staff only for this study. Collected data and all analysis of the data will adhere to HIPAA and institutional patient confidentiality requirements. More specifically, a coding system will be used for which a unique identifier will be assigned to each participant. Each subject whose data is collected will be assigned a unique study number. All electronic data will be managed using REDCap, a secure, web-based system that has user-level access control. Data will be stored for six years after completion of the study, per RSRB policy. This data will only be accessible to the PI and research staff. [contact] UR data security requirements will be followed (<http://www.rochester.edu/it/policy/index.html>).

15. DATA AND SAFETY MONITORING PLAN

Some identifiers will be collected such as name and electronic mail. All the identifiable data will be coded, removing the identifiers and assigning a unique study ID/code to protect the identity of the subject. Any sensitive data will not be collected.

Data Management and Transfer

[name] will access the data to conduct analyses. Data will be summarized and tables to be presented to Co-Investigators. [name] will be responsible for maintaining the security of the data.

All data will be stored on a URMC password protected computer only accessible by the investigator team. URMC password protected computers are only accessible by the P.I. and/or research staff. Electronic data will be managed using REDCap, a secure, web-based system that has user-level access control. Analytical datasets will be stored on secure servers that also limit access to the investigator team. All identifiers (names and contact information including emails) will be kept separately and will not include in any reports or potential publications. Data collected will be maintained securely with limited access. Records will be retained in accordance with regulatory, organizational and sponsor requirements, but no less than six (6) years following the completion of the research. Disposal of records will be done in such a manner that no identifying information can be linked to research data.

17. DATA ANALYSIS PLAN

We first will perform descriptive statistics to evaluate randomization success, nonresponses, and missing data. Mean and median will be presented for continuous variables, and frequencies will be presented for categorical variables. The outcome measures will be defined as (1) a binary variable of susceptibility to future vaping (0= definitely not, 1= probably not, probably yes, definitely yes) to ease interpretation of results, and (2) the overall susceptibility score aggregating three items. Bivariate analyses will be performed, followed by multivariable modeling to compare different message groups. Logistic regression model and the analysis of covariance (ANCOVA), respectively, will be performed to control for potential confounding, and inflated type I error rate will be adjusted in multiple testing. We will also assess differences within messages by theoretical construct (reward, self-efficacy, and social norms). **Power Analysis.** The goal of this pilot analysis is to provide preliminary data for future studies, including the possible effect size. Using the ANCOVA analysis for the power calculation, we expect the effect size to be 1.05 (standardized mean difference in the aggregated score) between message groups.

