students in a Title I school district in New Jersey (n=963; 66% Latinos, 37% White, and 36% African Americans) found a prevalence of 19% (compared to 6% for cigarettes) and 55% of students were susceptible to future vaping (no differences by race and ethnicity) (Tercyak et al., 2021). Despite the adverse health effects, high prevalence, and high susceptibility of future vaping among AYAs, there is a lack of effective messages and communication channels to prevent initiation. Overcoming the burden of vaping among AYAs demands affordable, accessible, and effective preventive solutions.

To date, we know little about whether messages can prevent vaping among AYAs and, if so, what messages and delivery formats may be most effective. One study found that chemical and anti-industry warning messages on television advertisements reduce intention to purchase e-cigarettes (Sanders-Jackson et al., 2015). Another study found that addiction warnings increase perceived harms and addictiveness of e-cigarettes and decrease thoughts about vaping, but only when these warnings were text-based – not on print advertisements (Mays et al., 2016). One limitation of both studies is the lack of representation of Latino and African American AYAs. This leaves a substantial gap in communication research for vaping prevention among racial and ethnic minority groups. As the adolescent vaping epidemic continues to grow, there is an urgent need to develop, test, and implement messages and communication channels for vaping prevention.

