4. STUDY DESIGN

This study is a randomized controlled trial (RCT) with a heterogenous sample of 360 African American and Latino adolescents (ages 12-17) who do not vape; equal representation of Latinos and African Americans (180 African American adolescents and 180 Latino adolescents). After completing a preliminary baseline survey, participants will be randomized in equal numbers and representation to receive one of four (4) theoretical-based graphic messages: 1) Financial Reward, 2) Health Reward, 3) Self-efficacy, and 4) Social Norms. These graphic messages were developed in a previous research phase (STUDY00005312) using participatory research methods. See Appendix for the messages. We will assess pre- and post-exposure measures on the susceptibility of future vaping-use among African American and Latino adolescents.

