5. INCLUSION AND EXCLUSION CRITERIA

Eligible individuals will 1) self-identify as African American/Black and/or Hispanic/Latino, 2) know how to read and speak English and/or Spanish, 3) be at least 12, but no greater than 17 years old, 4) have never used e-cigarettes, and 5) have access to a device that will be able to connect to the online survey (e.g., desktop, laptop, tablet, and/or smartphone). Exclusion criteria include: 1) not identifying as African American/Black and/or Hispanic/Latino, and 2) using e-cigarettes. Eligibility assessment will be conducted by study staff in the participant's language of preference, either English or Spanish.

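### Ordinary ANCOVA pools one error variance over four arms on a score likely to cluster at its minimum; HC3 standard errors would make the pairwise comparisons safer at no cost

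*Combined protocol and SAP*

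**What the plan says.** Section 17 of the combined protocol and SAP defines two outcomes: a binary susceptibility variable and "the overall susceptibility score aggregating three items". For these it plans that "Logistic regression model and the analysis of covariance (ANCOVA), respectively, will be performed to control for potential confounding", so ANCOVA applies to the score. It promises an adjustment for multiple testing without naming the method. It lists no pairwise contrasts and names no covariates. It mentions no robust or arm-specific variance, ordinal model or residual check.

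Section 8 gives the item responses as "1= definitely not, 2= probably not, 3= probably yes, 4= definitely yes". Section 4 states that "participants will be randomized in equal numbers and representation to receive one of four (4) theoretical-based graphic messages", with 360 in total. Section 5 requires that participants "have never used e-cigarettes". The only figure bearing on the score's distribution is in section 2, where a school survey found that "55% of students were susceptible to future vaping". No mean, SD or baseline-to-post correlation is given.

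**The concern.** Participants already at the lowest score cannot fall further. A message that works therefore moves only part of its arm, and the spread left after baseline adjustment can differ from that in an arm whose message does little. Ordinary ANCOVA averages the four arm variances and uses that average for every pair.

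In a two-arm trial with equal allocation this would do no harm, because the average is the quantity needed. With four arms, each pair also borrows the variance of the two arms not being compared, so equal allocation no longer protects it. Some pairwise intervals can then be too narrow and others too wide. This matters because section 17 describes the pilot's product as preliminary data, including a possible effect size, for future studies. The accuracy of the intervals around those effects is part of that product.

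**Working it through.** **Inputs from the document.** N = 360 in four equal arms, so 360/4 = 90 per arm. Three items scored 1 to 4 give a range of 3 to 12 if summed (3×1 to 3×4); the plan says only that they are aggregated.

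**Assumptions.** The share at the floor is 100% − 55% = 45%, with 70% as sensitivity; the survey was not restricted to never-users. The latent baseline-to-post correlation is 0.80, with 0.95 as sensitivity. ANCOVA adjusts for baseline score. Tests are two-sided at 0.05. Multiplicity is handled by Bonferroni over six pairs (0.05/6 = 0.0083).

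**The plan's own figure.** Section 17 gives a standardized difference of 1.05 with no alpha, power or SD, so nothing can be reproduced. Under the base assumption an untreated arm has mean 4.34 and SD 1.70. A difference near 1.05 then needs a working arm almost at the floor (mean 3.05, SD 0.27): (4.34 − 3.05)/√[(1.70² + 0.27²)/2] = 1.29/1.22 = 1.06. SDs of 0.27 and 1.70 hardly fit a common variance.

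**Formula.** For arms i and j with residual variances s², and ignoring small covariate imbalance:

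R = pooled SE / true SE = √[mean of the four s² ÷ mean of s²ᵢ and s²ⱼ]

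The true size of a nominal 5% test is 2[1 − Φ(1.96R)]. R below 1 means an interval that is too narrow.

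**Uniform shift along the latent scale** (simulation, 2,500 to 4,000 trials per scenario):

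- One message works, 0.8-point drop: residual variances 0.78 (working) and 1.39. The mean of four is (0.78 + 3×1.39)/4 = 1.24. Non-working pair: R = √(1.24/1.39) = 0.94, simulated coverage about 94%. Mixed pair: R = √(1.24/1.085) = 1.07, about 96%.
- Two work, 0.8 points: SE 13% too small for the non-working pair (coverage 91.2%), 24% too large for the working pair (98.5%), correct for mixed pairs.
- Two work, 1.2 points: 20% too small (88.1%) and 51% too large (99.5%).
- Three work, 1.2 points: mixed pairs 22% too small (87%), working pairs 53% too large (99.7%).
- Two work at about the plan's 1.05: residual variances 0.384 and about 1.686, mean 1.035. Non-working pair: R = √(1.035/1.686) = 0.78, coverage 87%. Working pair: R = √(1.035/0.384) = 1.64, coverage 99.9%. With three working, mixed-pair coverage is 86%.
- 70% at the floor, two working: 17% too small and 37% too large.
- No message works, or all four work equally: coverage 95% to 96%.

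**Partial response.** If only half of recipients respond, residual variances are 1.40 and 1.44 at correlation 0.80, and the distortion vanishes. At 0.95 they are 1.11 (working) and 0.65, and the direction reverses: the SE is 11% too small for the working pair and 14% too large for the non-working pair.

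A separate model lets each item drop one step with probability 5% in two arms and 30% in the other two. It gave residual SDs of 0.39 and 0.60. The mean variance is (0.36 + 0.152)/2 = 0.256. Stronger pair: R = √(0.256/0.36) = 0.84, size 9.8% (simulated 9.9%). Weaker pair: R = √(0.256/0.152) = 1.30, size 1.1% (simulated 1.2%). These sizes need nearly noise-free retesting. In further runs of the same structure, the weaker and stronger pairs rejected 2.5% and 7.3% at a within-arm baseline-to-post correlation of 0.97, and 4.6% and 5.8% at 0.90.

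**Overall range.** A further simulation with 45% or 70% at the floor gave rejection between truly equal messages of 0.6% to 11.7% with ordinary errors.

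**Familywise error.** With Bonferroni over six pairs, error over the truly equal pairs was 0.032 to 0.038 in four uniform-shift scenarios, and at most 0.044 in a noise-free item-drop extreme.

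**HC3.** In the uniform-shift and half-response scenarios, the mean SE was within about 4% of the true SE and coverage was 94% to 96%. Rejection between equal messages was about 4% to 6% in the further simulation, with no measurable power loss for unequal pairs. HC3 is not exact in the far tail: with two messages at about the 1.05 effect, mixed-pair error at nominal 0.0083 was 0.010 to 0.014.

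**The case against.** The strongest reply is that every figure rests on inputs the plan does not give: score distribution, SDs, correlation, covariates, contrasts and the multiplicity method. The survey behind the 45% mixed users with never-users, and the document does not say that its measure of susceptibility matches this score at its minimum. The largest distortions need large effects in two or three messages, or almost deterministic retesting. With one moderately effective message the SE error is only 3% to 8%. The point estimates are unaffected, the logistic analysis does not use the pooled variance, and section 17 calls this a pilot analysis. All of that stands, and it limits the severity.

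Three stronger readings are tempting but not supported:

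- **That any working message spoils the comparisons.** Messages must work unequally and the adjusted variances must differ. Equal effects give correct intervals, and in a two-and-two split the mixed pairs are correct. The test of no difference among all four messages is also sound when none exists.
- **That the direction is known**, for example that two effective messages will be called different too often. A uniform shift and a partial drop give opposite directions, and some patterns cancel. Nothing in the document says which applies.
- **That the promised multiplicity adjustment fails.** Under an assumed Bonferroni rule, familywise error stayed below 5%. When some messages differ, fewer than six pairs are truly equal, and that slack absorbs the excess. Individual pairs can still be off: at nominal 0.0083, error for a non-working pair reached about 0.04 when two messages had large effects.

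The unknown direction is itself a reason for a robust error, since nobody can say beforehand which intervals to distrust.

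**Conclusion.** The point holds as a free improvement of minor severity. The plan names a pooled-variance method for a bounded score that probably clusters at its floor, and the four-arm layout means that equal allocation does not protect the pairwise contrasts. Depending on the assumed response pattern, ordinary errors range from harmless to test sizes of about 1% to 12% and interval coverage of about 86% to almost 100%. This rests on 90 per arm, a summed score, 45% to 70% at the floor, adjustment for baseline, and assumed effects and correlations. The harm is confined to individual pairwise intervals and tests. It does not extend to the point estimates, to the overall test when messages do not differ, or, under the assumed Bonferroni rule, to familywise error above 5%.

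**What to change.** Add to section 17 that the ANCOVA point estimates for the score are kept, that all arm contrasts and confidence intervals for the score use heteroscedasticity-consistent (HC3) standard errors, and that the planned multiplicity adjustment is applied to those tests. Name the contrasts and the adjustment method at the same time, so that it is clear which tests are meant.

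The cost is a sentence or two and one software option. No participants or measurements are added, and the simulations showed no measurable loss of power at 90 per arm.

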18. FUTURE RESEARCH PLANS

We will report the results of this research in one or more publications in academic journal(s) to advance knowledge pertaining to effective communication with Latino and African American adolescents regarding vaping prevention. Additionally, we will disseminate our findings at national and international conferences. We have identified a request for applications

to pursue support for this line of research through the trans-NIH Tobacco Regulatory Science Program (RFA-OD-19-019). An FDA and NIH defined priority research area is to understand how to effectively communicate to the public and vulnerable populations regarding nicotine and the health effects of tobacco products.

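### Must the plan name in advance which between-message difference supplies the effect size for future studies?

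*Combined protocol and SAP*

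**What the plan says.** The design is a "randomized controlled trial (RCT) with a heterogenous sample of 360 African American and Latino adolescents (ages 12-17) who do not vape" (section 4). Under section 8, "participants will be randomized in equal number and representation to receive one of four (4) graphic messages". No control or reference message is described.

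Section 17 defines two outcomes, a binary susceptibility variable and an aggregated three-item score. It plans "multivariable modeling to compare different message groups", by logistic regression and ANCOVA respectively, and states that "inflated type I error rate will be adjusted in multiple testing". Differences by theoretical construct are to be assessed as well.

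The power paragraph in the same section gives the aim: "The goal of this pilot analysis is to provide preliminary data for future studies, including the possible effect size". It adds, for ANCOVA, that "we expect the effect size to be 1.05 (standardized mean difference in the aggregated score) between message groups". It gives no pair of messages, alpha, power or source for that figure, and no link from it to 360. Section 18 mentions a request for applications "to pursue support for this line of research through the trans-NIH Tobacco Regulatory Science Program".

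**The concern.** An effect size is one of the pilot's stated products, yet it is not tied to any contrast. In a trial with a control arm a reader could infer the comparison; here there are six candidate pairs on the score, six on the binary outcome, and further comparisons by construct.

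The promised adjustment is worded for tests. Adjusting p-values does not alter the point estimate of a pair chosen because it came out largest. Such an estimate is biased upward, and an ordinary 95% interval around it covers too rarely. Because sample size varies as one over the squared effect, a later study sized on an inflated difference would be too small. The only planning figure, 1.05, does not help to judge this, since its contrast and origin are not given.

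**Working it through.** **Inputs.** From sections 4 and 8: 360 participants, four messages, equal allocation, so 360/4 = 90 per arm and 4 × 3/2 = 6 pairs. From section 17: ANCOVA on the aggregated score and an expected standardized difference of 1.05. The residual SD is not given, so results are in residual-SD units. Assumed, because the plan does not give them: true best-to-worst spreads of 0.2, 0.3 and 0.5; pre-post correlations of 0.5 to 0.8; two-sided alpha 0.05 and 80% power.

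**The plan's own figure.** With no alpha, power or resulting sample size attached to 1.05, there is no calculation to reproduce. By the normal approximation, n per arm = 2(1.960 + 0.842)²/1.05² = 14.2, so 15, or 60 over four arms. Across exact t versions, with and without a Bonferroni division by six, the total is 60 to 96. So 360 exceeds what 1.05 needs, and there is no arithmetic error.

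**Precision.**
- SE of one adjusted mean = √(1/90) = 0.105. SE of a difference = √(2/90) = 0.149.
- Half-width of a 95% interval for one pair = 1.967 × 0.149 = 0.293.
- Tukey half-width over six pairs = 2.581 × 0.149 = 0.385.

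**Largest pair when all messages are equal.** The expected range of four standard normal values is 2.0588, so the expected largest difference is 2.0588 × 0.105 = 0.217 residual SD. An ANCOVA simulated on a skewed, discrete three-item score gave 0.215. In raw-SD units, multiplying by √(1 − r²) gives 0.188 at r = 0.5, 0.155 at 0.7 and 0.130 at 0.8.

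**If the largest pair were carried forward.** Simulation of four arm means, 90 per arm, 400,000 to 600,000 trials:

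| True means | Observed largest | True for pair picked | Ratio | Ordinary 95% CI coverage |
|---|---|---|---|---|
| All equal | 0.217 | 0 | – | 80% |
| Spread 0.2, one apart | 0.305 | 0.158 | 1.93 | 88% |
| Spread 0.2, even | 0.283 | 0.121 | 2.34 | 86% |
| Spread 0.3, one apart | 0.393 | 0.283 | 1.39 | 92% |
| Spread 0.3, even | 0.352 | 0.228 | 1.54 | 90% |
| Spread 0.5, one apart | 0.589 | 0.499 | 1.18 | 94% |
| Spread 0.5, even | 0.520 | 0.452 | 1.15 | 94% |
| Spread 1.05, one apart | 1.139 | 1.050 | 1.085 | 94% |
| Spread 1.05, even | 1.051 | 1.043 | 1.007 | 95% |

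Tukey intervals cover the picked pair in 95% or more of trials in every row. At 1.05, taken as residual SD, the implied sample-size error is 1.085² = 1.18 or 1.007² = 1.01.

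**Would shrinking the picked estimate be a clear gain?** Multiplying it by max(0, 1 − 1/F), with F from the ANCOVA group test, lowers the root mean squared error in the first five rows (from 0.236 to about 0.096 when all are equal). But at a spread of 0.2 it returns exactly zero in 29% (one apart) or 36% (even) of trials. It does worse at 0.4 evenly spaced (0.171 against 0.165) and at means of 0.5, 0.25, 0.25 and 0 (0.187 against 0.155). That is a trade-off.

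**The case for a change.** The strongest case for a change is that estimation, not testing, is the pilot's stated product, so the contrast and its interval are what most need stating. All four arms view an active message once, so small differences between them are plausible. The unsourced 1.05 cannot reassure anyone that selection bias will be minor. At small spreads the distortion is real, and one paragraph would remove the ambiguity without any extra participants.

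The arithmetic behind this stands, and so does the observation that no contrast is named. The consequence does not follow. It needs two steps that the plan does not contain: picking the largest pair, and sizing a next study on it. Section 18 names a funding call but gives no next design. With no control arm here, a later message-versus-control trial could not be sized from a between-message difference anyway. The spreads of 0.2 to 0.3 that produce the large ratios are assumptions from outside the documents.

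The other gaps are smaller than they look. Section 17 already ties the planning effect size to the aggregated score and to ANCOVA, so the outcome that supplies it is clear enough. Naming Tukey would only put a method to an adjustment already promised. The basis of 360 and of 1.05 would be useful documentation, but supplying it would not alter any analysis.

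**Conclusion.** No change is needed. Section 17 leaves the contrast for the effect size unspecified, but it contains no wrong rule or figure. Followed as written, the plan compares all message groups by ANCOVA with a multiplicity adjustment. An analyst would sensibly report the six adjusted differences with simultaneous intervals (half-width about 0.38 residual SD under Tukey) and would not plan from the largest alone.

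The 0.22 residual SD under equality is correct, but it measures a practice that the plan neither prescribes nor excludes. If that practice were adopted, the overstatement would be 1.4 to 2.3 times at assumed spreads of 0.3 to 0.2, about 1.15 to 1.18 at 0.5, and 1.01 to 1.085 at the plan's own 1.05. This conclusion assumes 90 analysed per arm, 1.05 read in residual-SD units, and the promised adjustment being carried through to the intervals.
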